## 9.1. Statistical Hypotheses

This study will evaluate if there is a significant difference in the change in plasma glucose level during exercise between Lyumjev and Humalog using either 50% or 100% reduction of basal infusion rates.

#### 9.1.1. Multiplicity Adjustment

There is no multiplicity adjustment in this study.

Participant Analysis Set	Description
Full analysis set	Participants who receive at least 1 dose of IP and have completed at least 1 MMTT procedure will be included in the analysis set for the PD analyses. Participants who receive at least 1 dose of insulin during the in-house period and have measurable insulin lispro concentrations will be included in the PK analysis dataset
Modified full analysis set	All participants who receive both treatments (Lyumjev and Humalog) for at least 1 basal rate reduction (either 50% or 100%) and receive the same dose and meal consumption. Participants who do not keep identical insulin lispro doses for Lyumjev and Humalog or have difference in the consumption of the meal for each visit/period will be excluded from the statistical analysis of the PK* and glucodynamic parameters
Safety analysis set	All participants who are exposed to at least 1 dose of IP. Participants
	will be analyzed according to the intervention they actually received

#### 9.2. Analyses Sets

Abbreviations: IP = investigational product; MMTT = mixed meal tolerance test; PD = pharmacodynamics; PK = pharmacokinetics.

\*For the MMTT PK parameters analysis, all participants who receive both treatments with an identical insulin lispro doses for Lyumjev and Humalog will be included.

## 9.2.1. Study Participant Disposition

A detailed description of the participant's disposition will be provided.

#### 9.2.2. Study Participant Characteristics

The participant's age, sex, weight, body mass index, height, race/subrace, duration of diabetes, smoking habits, or other demographic characteristics will be recorded.

#### 9.2.3. Treatment Compliance

Every attempt will be made to select participants who have the ability to understand and comply with instructions. Noncompliant participants may be discontinued from the study. The time and day of drug administration will be recorded. Drug accountability records will be maintained by the CRU.

The specifications in this protocol for the timings of safety, PK, and PD sampling are given as targets, to be achieved within the time windows described in the study specific CRF completion guidelines. Modifications may be made to the time points based upon the safety and PK information obtained. The scheduled time points may be subject to minor alterations; however, the actual time must be correctly recorded in the eCRF. Failure to obtain samples and perform protocol-specific procedures outside the allowable time window because of clinical issues, such as problems with venous access, technical problems with equipment, or problems with participant no-show for scheduled procedures, will not be considered a protocol deviation but the site will still be required to notify the sponsor in writing. Written documentation (e.g., a note-to-file) will have to be provided to the sponsor for all missing or delayed samples and procedures (regardless of reasons) to facilitate data reconciliation before study completion.

Any major modifications that might affect the conduct of the study, participant safety, and/or data integrity will be detailed in a protocol amendment.

# 9.3. Statistical Analyses

#### 9.3.1. General Considerations

Statistical analysis of this study will be the responsibility of Lilly or its designee. Any change to the data analysis methods described in the protocol will require an amendment ONLY if it changes a principal feature of the protocol. Any other change to the data analysis methods described in the protocol, and the justification for making the change, will be described in the SAP or the CSR.

Additional exploratory analyses of the data will be conducted as deemed appropriate. Analyses will be fully detailed in the SAP.

Insulin lispro concentration will be used for population PK analysis. Additionally, the study results may be pooled with the results of other studies for population PK analysis. This analysis and output will not be captured in the final CSR.

Insulin lispro concentration may be pooled with the results of other studies for population PK analysis purposes. This analysis and output will not be captured in the final CSR.

#### 9.3.2. Glucodynamic Analysis

#### 9.3.2.1. Glucodynamic Parameter Estimation

Participants who receive at least 1 dose of study intervention and have completed at least 1 MMTT procedure will be included in the analysis set for the PD analyses.

Data will be analyzed for the participants during each exercise and MMTT assessment.

During the exercise period, the change from baseline values **CCI** 

for each participant will be

calculated to derive the change in plasma glucose level from start to end of exercise.

The rate of plasma glucose during the exercise, the nadir plasma glucose, decremental AUC, for each exercise assessments will be calculated.

During the MMTT, the change from baseline values **CC** 

for each participant will

be calculated. The area under the baseline subtracted plasma glucose concentration versus time curve (incremental) (iAUC) will be calculated during the MMTT for each in-house period.

- The AUC from time zero to 30 minutes postmeal (iAUC0-30min)
- The AUC from time zero to 1-hour postmeal (iAUC0-1hour)
- The AUC from time zero to 2 hours postmeal (iAUC0-2hours)
- The AUC from time zero to 3 hours postmeal (iAUC0-3hours)
- The AUC from time zero to 4 hours postmeal (iAUC0-4hours)

In addition, the change from baseline maximum plasma glucose observed during the 4 hours postmeal ( $\Delta$ PGmax) and change from baseline 1-hour plasma glucose ( $\Delta$ PG1h and 2-hour plasma glucose after the start of the meal ( $\Delta$ PG2h) will be calculated. Other partial iAUCs may be calculated, as deemed appropriate.

The mean data will be presented by summary statistics and presented by treatment for those participants who received both treatments (Lyumjev and Humalog) with the same insulin dose (bolus dose for the MMTT or basal reduction) and meal consumption.

## 9.3.2.2. Glucodynamic Statistical Inference

Statistical analyses comparing PD parameters (described in Section 9.3.2.1) of Lyumjev versus Humalog during exercise with a basal reduction of either 50% or 100% and after the MMTT will be conducted on the modified full analysis set. The exercise and MMTT will be analyzed separately.

#### 9.3.2.2.1. Statistical Analysis of the Primary Endpoint Change in Plasma Glucose during Exercise

Changes in plasma glucose will be compared between Lyumjev versus Humalog from the start to the end of exercise during either 50% or 100% reduction of basal infusion rates.

For the primary endpoint, the change in plasma glucose will be analyzed using a mixed-effect model that includes treatment (Lyumjev, Humalog), sequence, period, and treatment as fixed effects and participant within sequence as a random effect. LSmeans, treatment differences in LSmeans, and the corresponding 90% CIs for the treatment differences will be estimated from the model. The p-value on the difference between LSmeans will be used to determine statistical significance.

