7. SAMPLE SIZE JUSTIFICATION

Approximately 32 participants may be enrolled to ensure that at least 28 participants complete the study.

This sample size will provide approximately 80% power to demonstrate a 14-mg/dL difference in the change in PG level from start to the end of the exercise between Lyumjev and Humalog, assuming no true difference in the change in PG level between Lyumjev and Humalog and a SD of 27.9 mg/dL with a 2-sided alpha-level of 0.1. Discontinued participants may be replaced to ensure that 28 participants complete the trial. A replacement participant will be assigned to the same treatment sequence as the participant being replaced.

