9.4.2 Pharmacodynamic Statistical Methodology

Primary glucodynamic endpoint

Changes in PG from the start to end of exercise will be statistically analyzed using a mixed– effect model. The model will include treatment (Lyumjev with 50% basal reduction, Lyumjev with 100% basal reduction, Humalog with 50% basal reduction, and Humalog with 100% basal reduction), sequence, period, timepoint, treatment-by-timepoint interaction as fixed effects, and participant-within-sequence as a random effect. Baseline (0 min timepoint) will be included as a covariate. The LS means, difference LS means between Lyumjev and Humalog for corresponding basal rate reduction, and corresponding 90% CIs, as well as the p-value, will be reported.

The p-value on the difference between LS means will be used to determine statistical significance.

Secondary glucodynamic endpoints

For the derived glucodynamic parameters iAUCs Δ PGmax, Δ PG1h, and Δ PG2h, a statistical analysis will be performed during exercise with a basal reduction, and after the MMTT independently. The modified full analysis population will be used for this analysis.

The parameters iAUCs during the MMTT and AUCs during exercise will be log-transformed before the statistical analysis. If negative values occur, the analysis will be performed on untransformed parameters. A mixed effects model will be used for this analysis. The model will include treatment (Lyumjev with 50% basal reduction, Lyumjev with 100% basal reduction, Humalog with 50% basal reduction, and Humalog with 100% basal reduction), sequence, and period as fixed effects, and participant-within-sequence will be included as a random effect. The LS means will be back-transformed to produce geometric means. The treatment geometric LS mean of each treatment, ratio of geometric means between Lyumjev and Humalog for corresponding basal rate reduction, and corresponding 90% CIs will be reported. The p-value will also be reported for the ratios. If the analysis is done on the untransformed parameters, the treatment LS means, difference in LS means between Lyumjev and Humalog for corresponding

basal rate reduction, and corresponding 90% CIs, as well as the p-value, will instead be reported. The treatment ratios and 90% CIs for the ratios will be calculated using the Fieller's theorem.

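### The Lyumjev–Humalog contrast within each basal reduction is tested against an error term pooled over both reductions, so its 90% CI can be too wide or too narrow

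*Protocol*

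**What the plan says.** Each participant has four in-house sessions, one for each combination of two insulins and two basal reductions (SAP sections 5 and 6; sequences ADBC, BACD, CBDA, DCAB).

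- **Protocol 9.3.2.2.1.** The primary model has a two-level treatment (Lyumjev, Humalog), with "sequence, period, and treatment as fixed effects and participant within sequence as a random effect". It has no term for the reduction and does not say whether the two reductions are fitted together or separately.
- **SAP 9.4.2 (version 2.0, primary analysis updated).** One model holds all four treatments, with sequence, period, timepoint, treatment-by-timepoint and a baseline covariate. Participant-within-sequence is the only random effect. The reported result is the "difference LS means between Lyumjev and Humalog for corresponding basal rate reduction". No participant-by-reduction term, session-level term or residual covariance over timepoints is named.
- **SAP 9.4.2 (secondary glucodynamic endpoints) and SAP 9.3.2 (exercise PK).** These use the same four-level, intercept-only form on derived parameters.
- **SAP section 7.** The sample size is said to give "approximately 80% power to demonstrate a 14-mg/dL difference in the change in PG level", with "SD of 27.9 mg/dL with a 2-sided alpha-level of 0.1".

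SAP section 3 states that the SAP supersedes the protocol's statistical considerations, so SAP 9.4.2 is the text to correct.

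**The concern.** A single participant intercept forces the same correlation between any two of a participant's four sessions. The two reductions are distinct strategies, one starting 60 minutes and the other 15 minutes before exercise. Two sessions at the same reduction may well be more alike than two at different reductions. That participant-by-reduction variation cancels in the reported difference, because both sessions of the pair share it, but part of it stays in the pooled residual and makes the SE too large.

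The opposite can also happen. If participants differ in their response to the two insulins, that variation belongs in the SE of the contrast, but the pooled residual takes in only part of it and the SE is too small.

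At stake are the width of the primary 90% CI, the p-value used to declare significance at 0.10, and the link between the analysis and the sample-size statement.

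**Working it through.** **Inputs.** From SAP section 7: 28 completers, difference 14 mg/dL, SD 27.9 mg/dL, two-sided alpha 0.10. From SAP section 6: the four sequences. Assumptions: 27.9 is the SD of the within-reduction paired difference (the SAP does not say), and there is one change value per session in steps 1 to 4. The interaction variances are not in the documents, so a range is shown.

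**1. The plan's own figure.** SE = 27.9/√28 = 5.27 and 14/5.27 = 2.66. A paired t test has 82.7% power with 27 df and 83.8% with 78 df; 26 completers already give 80.1%. The stated figure is therefore reproduced by a paired, within-reduction comparison. If 27.9 is instead a within-participant SD, power for one reduction is about 57%, and it reaches about 84% only when both reductions are averaged, which is not the reported contrast.

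**2. Error used and error needed.** Let s²e be the residual variance, s²R the participant-by-reduction variance and s²P the participant-by-product variance.

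- Each participant contributes three within-participant df. One carries an extra 2s²R and one an extra 2s²P.
- Pooled residual mean square: s²e + (2/3)(s²R + s²P).
- Mean square needed for the within-reduction contrast: s²e + s²P.

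The two agree only if s²R = s²P/2.

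**3. Participant-by-reduction variance only.** s²e = 27.9²/2 = 389.2. The reported SE is too large by k = √(1 + (2/3)s²R/389.2). With t = 1.665 (78 df), approximate coverage is 2Φ(1.665k) − 1 and approximate power is Φ(2.655 − 1.665k). The simulated values use the SAP sequences with 28 participants.

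| s_R (mg/dL) | k | Power, formula | Coverage, formula | Power, simulated | Coverage, simulated |
|---|---|---|---|---|---|
| 0 | 1.00 | 84% | 90% | 84% | 91% |
| 10 | 1.08 | 80% | 93% | 80% | 92% |
| 15 | 1.18 | 76% | 95% | 75% | 94% |
| 20 | 1.30 | 69% | 97% | 69% | 96% |

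**4. Participant-by-product variance only.** Let it be half of the paired-difference variance: s²e = s²P = 27.9²/4 = 194.6. Pooled mean square: 194.6 × 5/3 = 324.3. Needed: 389.2. k = √(324.3/389.2) = 0.913, and coverage is 2Φ(1.520) − 1 = 87% by formula, 86% simulated.

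**5. The primary model with timepoints.** The sampling times are redacted, so sets of 3, 4 or 6 times were assumed, with linear or random-walk change, an intercept only and no baseline covariate.

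- s²R = 0: coverage 77 to 86%, type I error 16 to 23%, rejection at 14 mg/dL 89 to 93%.
- s²R = s²e: coverage 85 to 92%, type I error 9 to 14%, rejection 83 to 87%.

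The intervals are mostly too narrow. In a further simulation of this structure, without a period term, the intercept-only model covered 67 to 88%. Adding only a participant-by-reduction effect lowered coverage in every setting, to 60 to 78%, with type I error of 22 to 40%.

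**6. Separate fits by reduction.** In the SAP sequences, a participant's two sessions at one reduction fall in periods 1 and 4 or in periods 2 and 3, and both insulin orders occur. The contrast is thus balanced for period. Error df: 28 paired differences less one treatment and two period contrasts = 25. The pooled model has 112 − 28 − 3 − 3 = 78. Simulated coverage is about 90% in all the scenarios of steps 3 and 4, and power is 82 to 83% whatever s_R is.

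**The case against.** A participant-within-sequence random effect is the conventional crossover model, and the protocol's sentence may already mean a separate fit for each reduction. On that reading the intercept absorbs the participant-by-reduction variation and there is no defect. This stands for the protocol, which does not settle the matter. It does not stand for SAP 9.4.2, which states the joint four-level fit.

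A reader might infer that the primary CIs are too wide and that the stated 80% power is lost. The documents do not support that, for four reasons:

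- No interaction variance is given. Under the assumptions above, power stays at about 80% up to an interaction SD of about 10 mg/dL.
- Participant-by-product variance acts in the opposite direction.
- The type of SD behind 27.9 is not stated, so the power figures have no firm baseline.
- The governing primary model has repeated timepoints. In the simulations its intervals were mostly too narrow, and rejection at 14 mg/dL never fell below 80%. That rejection rate comes with inflated type I error in most settings, so it is no reassurance.

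What remains is that the error term is not tied to the reported contrast. The secondary glucodynamic and exercise PK models share the structure with one derived value per session, so there the mechanism applies without the timepoint complication.

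**Conclusion.** The point holds as an incomplete random structure in SAP 9.4.2, not as a demonstrated loss of power. With one value per session, 28 completers and 27.9 mg/dL as the paired-difference SD, the 90% CI covers about 92 to 96% for an assumed participant-by-reduction SD of 10 to 20 mg/dL. Power is then about 80% down to 69%. Coverage is about 86% if half of the paired-difference variance is participant-by-product. For the primary model as written, the missing session-level structure pushes towards intervals that are too narrow, and the net direction cannot be determined from the documents. A fit within each reduction removes the dependence on these unknown variances at little cost, so the change is worth making.

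**What to change.** In SAP 9.4.2, analyse the single start-to-end-of-exercise change per session with treatment (Lyumjev, Humalog), sequence and period as fixed effects, the baseline covariate kept, and participant-within-sequence random. Fit this separately for the 50% and the 100% sessions. State the same in protocol 9.3.2.2.1, so that its two-level model can be read in only one way. Apply the rule to the within-reduction secondary glucodynamic contrasts (SAP 9.4.2) and exercise PK contrasts (SAP 9.3.2). State in SAP section 7 which SD 27.9 mg/dL is.

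Do not merely add a participant-by-reduction effect to the repeated-timepoint model. If that model is kept, it also needs a session-level random effect or a within-session residual covariance.

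Cost: SAP wording and a few lines of code. Error df fall from 78 to 25 before the baseline covariate. When no interaction exists, the average full CI width is about 17.8 instead of 17.5 mg/dL (17.8/17.5 = 1.02, about 2% wider) and power is about 83% instead of 84%.

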## 9.3.2.2.2. Statistical Analysis of the Secondary GD Endpoints

Changes in GD parameters during exercise and MMTT will be compared between Lyumjev versus Humalog during exercise with either 50% or 100% reduction of basal infusion rates.

Log-transformed iAUCs,  $\Delta PG_{max}$ ,  $\Delta PG1h$ , and  $\Delta PG2h$  will be evaluated to estimate geometric means, ratios of geometric means of insulin lispro within Lyumjev to Humalog, and their corresponding 90% CIs of the ratios using the mixed-effects model that includes treatment (Lyumjev, Humalog), sequence, period, and treatment as fixed effects and subject as a random effect. Analysis of iAUCs during the MMTT and AUCs during exercise will be based on untransformed endpoints, if negative values occurred. In this case, LSmeans, treatment differences in LSmeans, and corresponding 90% CIs for the treatment differences will be estimated from the model. The p-value on the difference between LSmeans will be used to determine statistical significance. The treatment ratios and 90% CIs for the ratios will be calculated using Fieller's theorem. Additionally, treatment differences in LSmeans, and corresponding 90% CIs may be estimated from the model for  $\Delta PG_{max}$ ,  $\Delta PG1h$ , and  $\Delta PG2h$  based on untransformed data.

The same model without log transformation will be used for the analysis of the rate of change in PG during the exercise period and exploratory GD time parameters. LSmeans, treatment differences in LSmeans, and the corresponding 90% CIs for the treatment differences will be estimated from the model. The p-value on the difference between LSmeans will be used to determine statistical significance. The treatment ratios and 90% CIs for the ratios will be calculated using the Fieller's theorem (Chow and Liu 2009).

Additionally, exploratory analysis may be conducted and will be defined in the SAP.

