3. INTRODUCTION

This SAP has been developed after review of the Clinical Study Protocol (final version dated 27 October 2021).

This SAP describes the planned analysis of the safety, tolerability, pharmacokinetic (PK), and pharmacodynamic (PD) data from this study. A detailed description of the planned TFLs to be presented in the clinical study report (CSR) is provided in the accompanying TFL shell document.

The intent of this document is to provide guidance for the statistical and PK/PD analyses of data. In general, the analyses are based on information from the protocol, unless they have been modified by agreement with Eli Lilly and Company. A limited amount of information concerning this study (e.g., objectives, study design) is given to help the reader's interpretation. When the SAP and TFL shells are agreed upon and finalized, they will serve as the template for this study's CSR.

This SAP supersedes the statistical considerations identified in the protocol; where considerations are substantially different, they will be so identified. If additional analyses are required to supplement the planned analyses described in this SAP, they may be performed and will be identified in the CSR. Any substantial deviations from this SAP will be agreed upon with Eli Lilly and Company and identified in the CSR. Any minor deviations from the TFLs may not be documented in the CSR.

This SAP is written with consideration of the recommendations outlined in the International Conference on Harmonisation (ICH) E9 Guideline entitled Guidance for Industry: Statistical Principles for Clinical Trials¹ and the ICH E3 Guideline entitled Guidance for Industry: Structure and Content of Clinical Study Reports².

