11. CHANGES FROM THE PROTOCOL SPECIFIED STATISTICAL ANALYSES

There were no changes from the protocol specified statistical analyses.

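### Protocol 9.3.2.2.2 logs three signed post-meal glucose changes (ΔPGmax, ΔPG1h, ΔPG2h) with no mandatory fallback, and SAP 9.4.2 gives them no scale

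*Protocol*

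**What the plan says.** **What the parameters are.** Protocol 9.3.2.1 introduces them after the iAUCs: "In addition, the change from baseline maximum plasma glucose observed during the 4 hours postmeal" (ΔPGmax), followed by the changes at 1 hour (ΔPG1h) and 2 hours (ΔPG2h). SAP 9.4.1 defines the same three.

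**Protocol 9.3.2.2.2, scale.** The iAUCs and all three changes are named together as log-transformed and "will be evaluated to estimate geometric means, ratios of geometric means of insulin lispro within Lyumjev to Humalog". The mention of insulin lispro looks carried over from the PK text; the parameters here are glucose.

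**Protocol 9.3.2.2.2, negative values.** The required switch reads "Analysis of iAUCs during the MMTT and AUCs during exercise will be based on untransformed endpoints, if negative values occurred". The three changes are not in it. Later in the paragraph comes "Additionally, treatment differences in LSmeans, and corresponding 90% CIs may be estimated from the model for" these three parameters on untransformed data. That sentence has no trigger and promises no p-value.

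**SAP 9.4.2.** The iAUCs and the three changes are listed for analysis. Then: "The parameters iAUCs during the MMTT and AUCs during exercise will be log-transformed before the statistical analysis". And: "If negative values occur, the analysis will be performed on untransformed parameters". No scale is given for the three changes.

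**Precedence.** SAP 3 says "This SAP supersedes the statistical considerations identified in the protocol; where considerations are substantially different, they will be so identified". SAP 11 says "There were no changes from the protocol specified statistical analyses". Neither document says what happens to a value whose logarithm does not exist; SAP 13.2 on missing data concerns listings only.

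**The concern.** A change from baseline can be zero or negative, and its logarithm is then undefined. The authors foresaw this for the iAUCs, which come from the same baseline-subtracted curve, but wrote no required rule for the three changes.

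Two things are at stake. First, the analyst can settle the scale after seeing the data. This matters more here because protocol 9.4 describes an unblinded sponsor team that may access data while the trial runs. Second, if the log scale is used, the lost values are not a random subset. They are the low post-meal changes, and protocol 2.2 reports better postprandial control with Lyumjev, so the loss should be heavier on Lyumjev. The log comparison would then be made on a treatment-dependent selection of values with broken Lyumjev–Humalog pairs. Small positive changes would also become large negative logs and inflate the residual variance.

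**Working it through.** **1. The texts side by side.**

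| | iAUCs, exercise AUCs | ΔPGmax, ΔPG1h, ΔPG2h |
|---|---|---|
| Protocol 9.3.2.2.2, main scale | log for the iAUCs; exercise AUCs named only in the fallback | log |
| Protocol 9.3.2.2.2, if negative | untransformed, required | no rule; untransformed analysis optional |
| SAP 9.4.2, main scale | log | not stated |
| SAP 9.4.2, if negative | untransformed, required | not stated |
| SAP 11 | no change declared | no change declared |

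**2. The plan's own figures.** There are none for these parameters. SAP 7 sizes only the primary endpoint: 28 completers, 14 mg/dL, SD 27.9, two-sided 0.10, about 80% power. Read as a paired comparison with noncentral t, that gives 80.1% at n = 26 and 82.7% at n = 28, so it reproduces closely, but it says nothing about post-meal changes. All that carries over is 28 × 4 = 112 planned sessions.

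**3. Share of values lost on the log scale, single time point.** Assume a normal change with mean m, between-participant SD s_b and within-participant SD s_w. Then S = √(s_b² + s_w²) and the share at or below zero is Φ(−m/S). All values of m and S are assumptions.

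- s_b = 30, s_w = 35: S = √2125 = 46.1. Mean 60: Φ(−1.30) = 10%. Mean 40: Φ(−0.87) = 19%. Mean 20: Φ(−0.43) = 33%.
- s_b = 20, s_w = 25: S = √1025 = 32.0. Mean 60: Φ(−1.87) = 3%. Mean 40: Φ(−1.25) = 11%.
- A mean rise of 2.58 SDs: Φ(−2.58) = 0.5%.

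**4. Direction.** Among positive values only, the mean is m + S·φ(m/S)/Φ(m/S). Take S = 50 and a true Lyumjev minus Humalog difference of −20 mg/dL.

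- Humalog 60, Lyumjev 40: losses 11.5% and 21.2%. Means among positives are 71.0 and 58.4, a difference of −12.6.
- Humalog 40, Lyumjev 20: losses 21.2% and 34.5%. Means among positives are 58.4 and 48.1, a difference of −10.3.

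The loss is unequal, and the difference shrinks toward zero.

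**5. Power for one Lyumjev–Humalog contrast.** Simulation with 28 participants, the four SAP 6 sequences, participant, period and four-level treatment effects, two-sided 0.10 and 1,500 trials per scenario. The raw scale uses all records; the log scale uses positive records only. Ranges are across repeated independent runs.

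| Humalog / Lyumjev mean | s_b / s_w | Lost, Humalog / Lyumjev | Power, raw | Power, log |
|---|---|---|---|---|
| 40 / 20 | 30 / 35 | 19% / 33% | 66–69% | 28–33% |
| 60 / 40 | 30 / 35 | 10% / 19% | 67–68% | 38–40% |
| 60 / 40 | 20 / 25 | 3% / 10% | 90–92% | 71% |

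In the first row about 16 of 28 pairs remain complete at each basal reduction.

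**6. The maximum is different.** ΔPGmax is the highest of several readings, so it is seldom non-positive. With S = 46.1 and eight assumed post-meal samples, serial correlation 0.7 gives about 1% (mean 40) and 3% (mean 20). Correlation 0.9 gives about 4% and 11%. Steps 3 to 5 therefore describe ΔPG1h and ΔPG2h far better than ΔPGmax.

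**The case against.** A reader might infer that, as planned, sessions in which glucose did not rise drop out of the product comparison. The documents do not support that, for four reasons.

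- The SAP supersedes the protocol and names only the AUCs as logged. A natural reading is that the three changes are not logged.
- The protocol paragraph itself allows an untransformed comparison of exactly these parameters, so log is not the only scale it mentions.
- Only the single parameter value would be undefined. The session stays in the other analyses, including the iAUCs, which have their own fallback. Nor does the description fit ΔPG1h and ΔPG2h, which can be at or below zero after an earlier rise.
- Deletion is inferred from the absence of a handling rule; no text states it.

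A reader might also set the simulated log-scale ratio (about 0.72 in the first scenario) against the true ratio of means of 0.50 and call the gap bias. One is a geometric and the other an arithmetic ratio, so the gap is not purely an effect of deletion.

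The assumed inputs are open to challenge too. A test meal of about 50 g carbohydrate (protocol 5.3.1.1) and an initial bolus chosen with a 25% reduction (protocol 4.1.2) both favour a rise, which points toward the smaller losses. The stakes are limited: the example given for the secondary endpoint is AUC0-4h.

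These points stand and narrow the finding. They do not remove it. An optional analysis with no trigger is not a rule, and a SAP that is silent on scale while declaring no change leaves the protocol's log analysis open as the operative reading.

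**Conclusion.** The concern holds in limited form. The protocol's required analysis of ΔPGmax, ΔPG1h and ΔPG2h is on a scale where some ordinary values do not exist, without a mandatory fallback, and the governing SAP does not say which scale applies. That gap is a matter of text and needs no assumption.

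The consequence is conditional. If the log analysis is followed and undefined values are left out, the loss would be treatment-dependent, would pull the comparison toward no difference and would reduce power. Its size rests on assumed normal changes with assumed means and SDs: about 0.5% to 33% of values per product for a single-time-point change, mainly ΔPG1h and ΔPG2h, and about 1% to 11% for ΔPGmax in the cases tried. The power figures illustrate those assumptions and do not predict this trial. The primary endpoint is analysed untransformed and the iAUCs have a fallback, so neither is affected by this gap. The change should be made, but it does not threaten the trial's main conclusion.

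**What to change.** In SAP 9.4.2, state that ΔPGmax, ΔPG1h and ΔPG2h will be analysed untransformed with the four-level treatment model already described there. Report the Lyumjev minus Humalog difference in LS means at each basal reduction, with 90% CI and p-value, as a required analysis. In SAP 11, list this as a change from protocol 9.3.2.2.2.

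This keeps all 112 planned values per parameter if 28 participants complete. It needs SAP wording only: protocol 9.3.1 requires an amendment only when a principal feature changes and sends other analysis changes to the SAP or CSR. The cost is that no geometric mean ratio is reported for these three parameters.
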